9.8. Exposure In Utero During Clinical Studies

While this should not be applicable, should it occur, see Section 9.2.2 for further details.

9.9. Clinical Laboratory Evaluations

Information will be entered in the case report form on whether or not measured, date of measurement, and measurement results and the local laboratory ranges for the following items.

The results will be reviewed and compared to the local accredited/certified laboratory's normal ranges. The visits at which these samples will be collected are shown in the schedule of assessments (Table 17.1).

The following safety laboratory evaluations are performed:

- **Serum Chemistry Panel**
 - Creatinine
 - Sodium (Na⁺)
 - Potassium (K⁺)
 - Chlorine (Cl⁻)
 - Blood urea nitrogen (BUN)
 - Glucose
- **Complete Blood Count (CBC) Panel:** Including Hemoglobin, Hematocrit, WBC, Platelet Count
- **INR** (only for subjects on VKA)
- **Urine pregnancy test** (e.g., dipstick test), for childbearing potential female subjects at Randomization, 3 months, 12 months, 24 months, and End of Treatment Visits.
- **Serum pregnancy test** at time of Screening for women of child bearing potential who are female subjects who are of child bearing potential.

A liver function panel (total bilirubin [conjugated/unconjugated performed when total serum bilirubin \geq 2 mg/dL], ALT, AST, ALP) will be performed at Screening (only if a recent, within the 15 days before randomization, is not available), and at the 6 Month and 12 Month Visits.

All other assessments are collected from local laboratory results for tests done as part of routine care. Local laboratory assessments are used for parameters required to verify eligibility and for parameters that require monitoring according to local routine.

9.10. Vital Signs

Blood pressure and heart rate will be measured at all specified visits (Table 17.1) after the subject has been resting at least 5 minutes in a sitting position, along with height (only at randomization), body temperature, and body weight.

9.11. Electrocardiograms

The ECG will be recorded after the subject has rested in a recumbent position for 5 minutes or more. The date performed, results, and any clinically significant findings for will be recorded in the case report form.

If the ECG is not performed for any reason, the date and reason will be recorded in the case report form.

9.12. Physical Examinations

The Investigator or a licensed study team member will perform targeted physical examinations according to [Table 17.1](#). As stated earlier, height is only needed once, usually at Screening.

A physical examination will consist of assessment of each of the relevant (cardiac, pulmonary, gastrointestinal, dermatologic) major body systems. If a system is not assessed, the Investigator or designee will note the reason in the source documents. Assessment of other systems, including neurological, is not required per protocol, unless determined as necessary per investigator discretion for further evaluation of a suspected AE (eg., Stroke or TIA), or suspected outcome event.

10. OTHER ASSESSMENTS

10.1. Healthcare Resource Utilization

Data for each hospitalization post TAVI but non-TAVI procedure related that are due to cardiovascular causes (such as shock, arrhythmia, cardiac rupture, stroke, aneurysms, stent occlusions, etc.), including data on admission and discharge dates, hospital ward (e.g., emergency department, intensive care unit, cardiovascular ward), admission diagnosis and status post TAVI will be collected.

- Bleeding
- Ischemic stroke
- SEE
- Myocardial infarction
- Valve thrombosis
- Other cardiovascular causes

10.2. Perception Anticoagulant Treatment Questionnaire (PACT-Q)

The Perception of Anticoagulant Treatment Questionnaire (PACT-Q) was developed to assess subjects' expectations of, and satisfaction with their anticoagulant treatment. The psychometric properties of the PACT-Q have been reported previously. The PACT-Q consists of two modules. The first module, PACT-Q1, contains 7 items, each individually scored from 1 to 5, with higher score indicating higher subjects' expectation for their treatment. The second module, PACT-Q2, is constituted of two dimensions: Convenience (11 items) and Anticoagulation Treatment Satisfaction (7 items). Items in the Convenience dimension are reversed scored, summed and rescaled on a 0 to 100 scale such that the higher the score indicates a treatment to be more convenient and less burdensome as perceived by the subject. Items in the Anticoagulation Treatment Satisfaction dimension are summed and rescaled on a 0 to 100 scale. Higher score indicates higher satisfaction with anticoagulation treatment.

The PACT-Q1 will be administered to study subjects at randomization. The PACT-Q2 will be administered to study subjects at 3 months and either 12 months or the EOT whichever comes first. A copy of the PACT-Q1 and PACT-Q2 will be provided to the sites.

10.3. EuroQoL (EQ-5D-5L) Questionnaire

The EQ-5D-5L is standardized measure of health status developed by the EuroQoL Group in order to provide a simple descriptive profile and a single health status index. The EQ-5D-5L consists of two measures: 1) the EQ-5D-5L descriptive system and 2) the EQ Visual Analogue Scale (EQ VAS). The EQ-5D-5L descriptive system asks the subject to provide rating on each of the five dimensions of health: mobility, self-care, usual activities, pain/discomfort and anxiety/depression. The EQ VAS records the subject's overall health on a 0 to 100 analogue scale anchored from "best imaginable health state" to "worst imaginable health state".

The EQ-5D-5L is designed for self-completion by study subjects and takes only 1 to 2 minutes to complete. The EQ-5D-5L will be administered for study subjects at randomization, 3 months and either 12 months or the EOT whichever comes first. A copy of the EQ-5D-5L will be provided to the sites.

11. STATISTICAL METHODS

11.1. Analysis Sets

In the following subsections only the analysis sets for the statistical analyses of efficacy and safety parameters are defined. Other analysis sets (e.g., health economics outcome research [HEOR]) will be defined in the Statistical Analysis Plan (SAP) as needed.

11.1.1. Intention-to-treat Analysis Set

The *Intention-to-treat Analysis Set (ITT)* consists of all randomized subjects irrespective of whether they received a single dose of study Edoxaban or VKA or not.

Analyses will be based on the randomized treatment regimen even if a subject inadvertently receives the incorrect drug(s) or dosage or has his/her Edoxaban dose adjusted (decreased/ increased) one or more times during the study. The reference date for consideration of endpoints is the date and time of randomization.

11.1.2. Modified Intention-to-treat Analysis Set

The *modified Intention-to-Treat (mITT) Analysis Set* consists of all randomized subjects who received at least one dose of study Edoxaban or study VKA according to IXRS assignment.

Analyses will be based on the randomized treatment regimen even if a subject inadvertently receives the incorrect drug(s) or dosage or has his/her Edoxaban dose adjusted (decreased/ increased) one or more times during the study. The reference date for consideration of endpoints is the date and time of first intake of study Edoxaban or study VKA.

11.1.3. Per Protocol Analysis Set

The *Per Protocol Analysis Set (PP)* consists of all randomized subjects who received at least one dose of the study regimen according to IXRS assignment and do not have any of the following major protocol violations:

- o A major violation of the inclusion criteria
- o An unequivocal violation of the exclusion criteria

The list of major violations will be finalized before database lock. The list and the exclusions will be confirmed in a blinded way, i.e., without knowledge of the randomized study regimen and of the clinical outcomes.

Analyses will be based on the randomized treatment regimen, even if a subject inadvertently receives the incorrect drug(s) or dosage or has his/her Edoxaban dosage adjusted (decreased/ increased) one or more times during the study. The reference date for consideration of endpoints is the date and time of first intake of study Edoxaban or study VKA.

11.1.4. Safety Analysis Set

The *Safety Analysis Set (SAF)* consists of all randomized subjects who received at least one dose of the study Edoxaban or study VKA according to IXRS assignment.

Analyses will be based on the randomized treatment regimen, even if the subject's Edoxaban dosage is adjusted after randomization, unless a subject inadvertently receives the incorrect drug(s) or dosage during the entire study, in which case the subject will be grouped according to the treatment actually received.

Note: This SAF analysis set will be used for the safety parameters (e.g., adverse events, vital signs, laboratory parameters, etc.) as described under Section 9.

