9.4. Timing of Adverse Event Reporting

All AEs must be recorded and reported from the stated starting point of the clinical trial (immediately after signing ICF) including AEs taking place during the administration of other drugs. Even if the subject has not yet received the investigational treatment, untoward medical occurrences have to be treated as AEs.

The period of AE reporting is defined as follows:

AEs that occur within 30 days after the last dose of the assigned study treatment, which are reported to the Investigator (regardless of the date of a Follow-up Visit) must be recorded in the eCRF.

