11.5.1. Adverse Event Analyses

Adverse events meeting the criteria defined in Section 9.3 will be recorded in the eCRF and coded by system organ class and preferred term using the Medical Dictionary for Regulatory Activities (MedDRA), version 19.1 or newer.

Treatment-emergent adverse events (TEAEs) are defined as events which start on or after any first dose of the assigned study medication regimen or started prior to but then worsened after any first dose of the assigned study medication regimen. An AE that occurs more than 30 days after the date of the last dose of the assigned study medication regimen will not be counted as a TEAE.

TEAEs will be summarized by treatment group. The incidence of TEAEs will be presented by treatment group, by relationship to the assigned study regimen, and by severity. If more than one AE is coded to the same preferred term for the same subject, the subject will be counted only once for that preferred term using the greatest severity and strictest causality for the summarization by severity and causal relationship. Frequent TEAE (reported by at least 5% of subjects in any treatment group) will be summarized by regimen group.

The incidence of death, SAEs, drug-related SAEs, and AEs leading to permanent discontinuation of the assigned study regimen will be summarized. All AEs meeting the criteria defined in Section 9.3.4 will be included in a data listing and a listing to display the coding of AEs will be prepared as well.

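### Minor: safety-set entry and the TEAE window are tied to the assigned drug, so the as-treated rule for subjects on the wrong drug throughout has no one to act on

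*Combined protocol and SAP*

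**What the plan says.** Section 11.1.4 holds an entry rule and a grouping rule. By the entry rule the SAF "consists of all randomized subjects who received at least one dose of the study Edoxaban or study VKA according to IXRS assignment"; the synopsis repeats this. By the grouping rule subjects are analysed as randomized "unless a subject inadvertently receives the incorrect drug(s) or dosage during the entire study". The consequence for a subject of that kind follows: "in which case the subject will be grouped according to the treatment actually received".

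The modified ITT set (mITT, Section 11.1.2) has the same entry condition but always analyses as randomized. Section 11.5 bases all its safety analyses on the SAF.

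Section 11.5.1 defines TEAEs as "events which start on or after any first dose of the assigned study medication regimen", or events that "started prior to but then worsened after any first dose of the assigned study medication regimen". An AE "more than 30 days after the date of the last dose of the assigned study medication regimen will not be counted as a TEAE".

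Section 15.5 asks that safety data be collected from subjects given the wrong treatment, provided they had at least one administration of study drug. Section 11.1 states that "only the analysis sets for the statistical analyses of efficacy and safety parameters are defined" in its subsections and leaves other sets to the SAP. Section 11.10 says a SAP will be written with the definitions for analysing the efficacy and safety data.

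**The concern.** An as-treated rule exists so that harms are shown under the drug that was taken. Here the entry rule removes, before grouping starts, the subjects whom the grouping rule is meant to move. The rule is also what should set the SAF apart from the mITT set; without its wrong-drug part the two sets coincide.

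At stake are the adverse event, laboratory, vital-sign, ECG and physical-examination data of anyone who took only the other arm's drug. Section 15.5 wants these data collected, but as written they have no place in the Section 11.5 tables.

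**Working it through.** The plan states no figure on this point, so there is none to reproduce. The check applies each rule to every possible treatment history.

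**Step 1: SAF entry against the as-treated trigger.** There are two possible assignments and five histories for each, giving 2 × 5 = 10 cases. The pattern is the same for either assignment.

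| Drugs taken | Enters SAF | Wrong drug throughout | Both |
|---|---|---|---|
| None | no | no | no |
| Assigned drug only | yes | no | no |
| Other arm's drug only | **no** | **yes** | no |
| Assigned, then other | yes | no | no |
| Other, then assigned | yes | no | no |

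Two of the 10 cases are wrong drug throughout (one per assignment). Neither enters the SAF, so the overlap is 0 of 10.

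**Step 2: the dosage part of the rule.** If assignment means the drug alone, a subject on the right drug at a wrong dosage throughout is in the SAF. Regrouping then changes nothing, because there are only two regimens. If assignment also covers dose (Section 5.2.5 has Edoxaban dosed through the IXRS), that subject is outside the SAF too. On either reading no one changes arm, so the SAF and the mITT set have the same members in the same arms.

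**Step 3: the TEAE window.** The start needs a first dose of the assigned regimen and the end needs a last dose of it. A subject on the wrong drug throughout has neither date, so no event can qualify. Section 11.2 bases AE percentages on all subjects in the analysis set and regimen. Correcting SAF entry alone would therefore put such a subject in the denominator with no possible TEAE. Both passages need the change.

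**Step 4: possible size.** Section 11.9 plans about 1400 subjects at 1:1, so 1400 / 2 = 700 per arm. Adding k subjects to an arm of 700 moves an AE percentage by at most k / (700 + k). The documents give no count; the values of k are assumptions.

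- k = 1: 1/701 = 0.14 percentage points
- k = 2: 2/702 = 0.28 percentage points
- k = 5: 5/705 = 0.71 percentage points

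These are ceilings. They are reached only if all the added subjects have the event and no one else in the arm does, or the reverse.

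**The case against.** **The intent is evident.** The grouping clause directs that wrong-drug subjects be shown under the drug received, and an analyst giving effect to every clause would admit them. That stands as to intent. It does not change the entry wording, and it does not help with the TEAE window, where the word assigned would still exclude their events.

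**The SAP can correct it.** This also stands. From the sentence in Section 11.1 a reader might infer that the SAP is barred from redefining the safety set. The documents do not support that: Section 11.10 gives the SAP the definitions for efficacy and safety analysis, and Section 15.4 allows changes to the planned analysis to be documented there. What remains is that no supplied text makes the correction.

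**Data might seem to be lost at collection.** Section 9.4 refers to "AEs that occur within 30 days after the last dose of the assigned study treatment", and a reader might infer that wrong-drug subjects' events go unrecorded. That is not supported. Section 9.4 also records events from consent, including those during administration of other drugs. Section 9.5.1 reports events for as long as the subject remains in the study, and Section 15.5 covers wrongly treated subjects. Only tabulation is affected.

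**Assigned does useful work in Section 11.5.1.** It keeps standard-of-care VKA after Edoxaban from extending the window. That is fair, and the fix must preserve the protection. How transition-kit Edoxaban is counted at end of treatment is a separate question that exists under the present wording; it is no part of this point.

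**The case is rare.** Cross-over is not permitted (Section 5.1.2), Edoxaban kits are allocated by the IXRS (Section 5.2.2) and the first dose is supervised (Section 5.5). This stands, although VKA comes from sites or by prescription (Sections 5.2.2 and 5.3), so kit control covers Edoxaban only.

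**Conclusion.** The fault is real as written, and minor. On the plain reading of the entry condition, the wrong-drug part of the as-treated rule applies to no one, and the TEAE definition would leave such subjects without events even if they were admitted. The conclusion rests on reading that condition as limiting which doses count.

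The number affected is unknown, probably very small and possibly zero. With 1 to 5 subjects assumed, the ceiling is 0.14 to 0.71 percentage points on any AE rate in an arm of 700.

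A reader might infer that the bleeding or mortality comparison is compromised. It is not: the main analyses of NACE, ISTH major bleeding and the other adjudicated endpoints use the ITT set (Sections 11.2, 11.4.1 and 11.4.2). Only the Section 11.5 safety tables would change.

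**What to change.** - **SAF entry (Section 11.1.4 and synopsis).** Admit every randomized subject with one or more doses of either study anticoagulant, study Edoxaban or study VKA. Delete the condition on IXRS assignment and keep the as-treated grouping rule. Section 11.2 already defines its initial-to-final-dose period without that condition, so the wording has a model in the protocol.
- **Locally supplied VKA.** State that VKA taken during the treatment period in place of assigned Edoxaban counts as study VKA for this purpose. Otherwise an Edoxaban-assigned subject who took only prescribed VKA could still be left out.
- **TEAE window (Section 11.5.1).** Run it from the first dose to 30 days after the last dose of the study medication actually received in the treatment period. State that post-study, transition or post-discontinuation standard-of-care anticoagulant does not extend it.

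The cost is a few sentences in the protocol, carried into the SAP. No new data are needed, because study drug start and stop dates are already captured in the eCRF (Section 5.8). There are two downsides. The SAF and mITT sets may then differ slightly. For subjects on the wrong drug for only part of the study, AEs from that phase would stay under the randomized arm, because the as-treated rule covers only error lasting the whole study.

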11.2. General Statistical Considerations

All analyses will be performed on observed data only. No missing data will be imputed. Data on subjects who do not reach a specific endpoint will be censored in the corresponding statistical analyses.

Raw data will be presented with the exact precision (decimal points) with which it was collected.

The p-values will be presented in the end-of-text tables exactly as they are in supporting statistical documents (4 decimal points). The text and in-text tables will display p-values with three decimal places, as long as the decision for statistical significance will not be changed by rounding.

The number of decimal places to display for calculated data will be determined by the scale of measurement. No decimal places will be displayed if the smallest calculated value is ≥ 100 ; one (1) decimal place will be displayed when all calculated values are within the interval (10, 100), with 10 being inclusive; two (2) decimal places will be displayed when all calculated values are within (1, 10), with 1 being inclusive; and so on for even smaller scales of measurement. Percentages will be reported with exactly one decimal place.

For continuous variables, statistical summaries will include n (number of subjects with non-missing data), mean, median, standard deviation, minimum, and maximum. Means and medians will be displayed to one more decimal places than the raw or calculated data; standard deviation and other dispersion statistics will have two more decimal places; and minimum and maximum values will be displayed to the same number of decimal places as the raw or calculated data.

For categorical variables, statistical summaries will include counts and percentages. Percentages will be reported with exactly one decimal place. In general, percentages are based on the total number of subjects with information available (i.e., non-missing data). For AE and incidence-based analyses, percentages will be based on the total number of subjects in the analysis set of interest and in that treatment regimen.

Definition of terms:

'Overall Study Period': This period is defined as the time from the reference date up to an estimated Month 36/EOT (Visit 8).

'Overall Study Period + 30 days': This period is defined as the time from the reference data up to an estimated Month 36/EOT (Visit 8) + 30 days, i.e., to Month 37 (post-treatment FU visit).

'Initial dose to Final Dose + 30 days': This period is defined as the time-period between the date and time of initial dose of study Edoxaban or study VKA and the date and time of final dose of study Edoxaban or study VKA + 30 days, including study regimen interruptions.

Follow-up is censored at the last date of known follow-up status in subjects with incomplete follow-up. Investigators are instructed to complete follow-up as much as possible irrespective of changes or discontinuation of study medication.

When using the ITT analysis set, the reference date is the date and time of randomization, whereas in mITT and PP analyses, the reference date is the date and time of first intake of study Edoxaban or study VKA.

The main analyses of adjudicated primary and secondary exploratory endpoints (Section 7.2, Section 7.3, and Section 7.4, respectively) will be based on ITT analysis set and takes the first adjudicated event during the 'overall study period' into account.

However, in supplemental analyses, other combinations of analysis sets and analysis periods may be considered to evaluate the robustness of the main analyses on adjudicated safety or efficacy endpoints. Details on these analyses will be described in the SAP.

11.3. Study Population Data

Subject disposition will be summarized for each randomized treatment regimen and in total for the ITT analysis set. The number of subjects for each defined analysis set by treatment regimen will also be tabulated.

The demographic and baseline characteristics including baseline disease status will be summarized descriptively by treatment regimen for the ITT, mITT, PP, and SAF analysis sets.

Exposure to study drugs (Edoxaban, VKA, P2Y₁₂ antagonist, and ASA) will be summarized using descriptive statistics by treatment regimen for the mITT, PP and SAF analysis sets. Interruptions and permanent discontinuations (see Section 5.8) will be summarized by treatment group for the same analysis sets.

The time in therapeutic range (TTR) (INR: 2.0 to 3.0, numbers inclusive) [Japan: 1.6 to 2.6 in subjects age ≥ 70 (numbers inclusive)] will be estimated for each subject randomized to the VKA-based antithrombotic regimen using the interpolation method of Rosendaal.²⁶

